#### **4.4** Separation Visit

The last scheduled visit at 72 weeks represents the final collection of data to be included for the primary and secondary analyses. Subjects will stop coded study medications at

that time. In order to provide participants with a summary of their care, disclose their treatment group and provide future treatment recommendations, a Separation Visit has been planned. Since disclosing the treatment group requires breaking the blind, the Separation Visit cannot be scheduled until the database is locked. It is anticipated that database lock will occur approximately 4 to 6 months after the last participant (studywide) has completed the last scheduled visit, which may be as long as 18 months after the first study participants have their last scheduled visit.

The Separation Visit will be scheduled after the database has been locked and the treatment groups have been made available to the clinical centers.

The Separation Visit will be optional for the participant. At this visit the participant will be provided with:

- 1. Treatment group.
- 2. Graphical history of PSA.
- 3. Graphical history of the AUA Symptom Score.
- 4. Recommendations for future treatment.
- 5. Information on obtaining the eventual published results of the trial.
- 6. An opportunity to ask questions about the trial.

If the participant prefers, the summary can be mailed to him.

#### 5.0 TREATMENT PLAN

#### 5.1 Summary of Treatment Plan

CAMUS participants will receive a study medication or matched placebo (see Section 3.3). All participants will take one gelcap daily for the first 24 weeks, two gelcaps daily in the second 24 weeks and three gelcaps daily in the last 24 weeks. The placebo will be matched for appearance with the therapy.

Serenoa Repens and matching placebo will be supplied as "dark colored" gelcaps in blister packs.

#### 5.2 Retitration and Rechallenge with Study Medications

A participant may experience a symptomatic side effect or other abnormality (e.g., a laboratory abnormality) that either he or the investigator believes may be related to the study medication and require withdrawal. Investigators will consider the possibility of a study medication side effect especially in the event of a new, persistent abnormality in any blood test, particularly one that would have excluded a participant's enrollment at baseline, or in the event of new evidence of myocardial infarction or ischemia on the periodic study EKGs. In these circumstances, it may be prudent to attempt a rechallenge of study medication in order to ascertain more evidence of causality and to better assess severity of the adverse effect. Whether or not to perform a rechallenge is the decision of the site principal investigator; obviously, it would be inadvisable to rechallenge a patient who had a serious reaction with a high likelihood of being related to the study medication.

In the event that there is an interruption of therapy and the participant does not take the study medication for at least 14 days (e.g. due to compliance problems, lost medication, physician stopping drug for mild intolerance or minor adverse event), the participant may be retitrated on the medication.

In the event that the participant experiences a moderate or severe adverse event and it is the physician's medical judgment that the participant should be restarted on the study medication and the physician has contacted the Clinical Review Committee and received approval, the participant may be rechallenged.

Retitration or re-challenge should utilize the same kit of medication that the participant has been using or a new kit for that participant may be issued (contact the Drug Distribution Center to request an additional kit if necessary). The participant should be dosed in the following manner. The participant should start at the lowest dose (1 capsule daily) for at least 1 week (longer if physician/participant desires) and then add 1 capsule per day each week until the previous maximum dose (2 gelcaps/day or 3 gelcaps/day) is

reached or the participant becomes intolerant of the medication. Investigators may suggest that participants spread doses out over the day to increase tolerability. If, in the medical judgment of the physician (as in the case of a severe adverse event or reaction) medication should not be continued, or in the event that a participant does not want to continue the medication, the medication does not have to be restarted.

It should also be noted that, under the principle of intention-to-treat, even if a participant will no longer continue to take his study medication, he should be encouraged to continue his study visits and all data (with the exception of pill counts) should be collected.

The procedure for re-challenge will vary with the specific clinical situation, but should follow the general guidelines below:

- The date of last study medication use by the participant should be recorded on the study drug administration form. All study medications should be discontinued.
- 2) The site principal investigator should determine if it is safe to re-challenge the participant. If so, re-challenge should be discussed with the participant.
- 3) If the participant agrees, he should remain off study medication until all symptoms or abnormalities have stopped (it may be very useful to create a daily diary for the participant to use during this time). The participant should remain off study medication for at least one additional week (to ensure that there is stability in the absence of the symptoms).
- 4) The participant should be followed closely (at least weekly) for recurrence of the symptoms or abnormalities; he should also be advised to contact study staff if his symptoms recur. Again, it may be useful to continue use of a daily diary for the participant. If symptoms recur after restarting the study medication, the investigator should consider withdrawing the participant permanently from study medication. If the symptoms/abnormalities do not recur, the participant may continue in the study following usual study procedures.

5) NOTE: If, after withdrawing the study medication, the participant's symptoms/abnormalities do not diminish, the investigator may wish to discuss re-challenge with the participant (since the symptoms may have been due to some cause other than the study medication). Careful monitoring of the participant should be observed during this re-challenge period. When assessing the potential causal relationship between the symptom/abnormality and the study medication, remember that the phytotherapy contains many fat-soluble constituents, so that the participant may have detectable tissue levels for several weeks after the medication is discontinued.

If subjects do not redevelop the side effect on re-challenge, they can remain on the final dose for that phase of the study until they have completed 24 total weeks of therapy at that dose, and then be escalated as called for in the protocol, unless they are already at triple dose, in which case they will be at the end of the study.

If on re-challenge, a participant once again develops the same side effect at a higher dose of study medication, but has tolerated a lower dose, he can be dropped back to the lower, tolerable dose for the rest of the study.

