#### 1.0 INTRODUCTION

#### 1.1 Study Rationale

The long-term efficacy and side effects of over-the-counter phytotherapies for men with lower urinary tract symptoms attributable to BPH are unknown, despite wide use of these agents by older men for maintaining "prostatic health." The overall goal of this study is to compare the efficacy of a widely available phytotherapy, extract of Serenoa Repens, against placebo in terms of impact on lower urinary tract symptoms. The phytotherapy selected for study has demonstrated short-term efficacy at relieving lower urinary tract symptoms with minimal side effects in a number of clinical trials. However, a recent NIDDK/NCCAM supported trial of Serenoa Repens at the 320 mg daily dose versus placebo did not demonstrate efficacy in terms of symptom reduction over 12 months of follow-up. As a result, this study is being conducted to compare higher-than-standard (double and triple) doses of this agent to determine its short-term effect on lower urinary tract symptoms and other parameters of BPH disease severity, and whether there is sufficient short-term efficacy and tolerability to merit testing for long-term efficacy in a long-term trial focused on the prevention of BPH progression. Because the study arm will use doses of this agent higher than generally used, participants will be monitored closely for toxicity/tolerability and have their doses slowly increased at 24-week intervals.

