#### 2.0 OBJECTIVES

#### 2.1 Primary objective

The primary objective of CAMUS is to determine if Serenoa Repens reduces the AUA symptom score compared to placebo over 72 weeks of treatment and is well tolerated.

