#### 8.2.2 Analyses of the Primary Study Endpoint

The primary endpoint of this study is efficacy as determined by the change in AUA symptom score at 72 weeks. A two-group t-test will be used to compare the phytotherapy arm against placebo. A one-sided significance level of 0.05 will be used.

Mixed models repeated measures analysis will be performed to compare the phytotherapy arm with placebo over time (baseline, 24 weeks, 48 weeks and 72 weeks). This technique will control for intra-patient variation. The final covariance structure to be used in these models will be selected after all of the data have been collected. A significance level of 0.05 will be assumed for these longitudinal comparisons. Regarding multiple comparisons, differences between the two treatment groups with respect to the change in the primary endpoint from baseline to 24 weeks, baseline to 48 weeks, and baseline to 72 weeks will be examined to determine if they are significantly different from zero. If these differences are significantly different from zero, comparisons between specific timepoints (48 weeks versus 24 weeks, 72 weeks versus 48 weeks, and 72 weeks versus 24 weeks) for the primary endpoint will be performed. The Hochberg step-up method will be used for each set of these multiple comparisons. (Hochberg, 1990)

An additional analysis that will be performed using the primary endpoint is a comparison between the phytotherapy and placebo arms with respect to the proportion of participants who achieve at least a 3 point difference (improvement) in the AUA symptom score. These proportions will be compared using Fisher's exact test. A one-sided significance level of 0.05 will be used for this comparison.

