Complete blood counts and serum chemistry measurements will be categorized by severity grade from the NCI Common Toxicity Criteria. For each participant and each time period on a dose level (1-24 weeks = level 1, 25-48 weeks = level 2, 49-72 weeks = level 3), the most severe grade of a laboratory level will be taken. For each dose level and laboratory measure, the proportions of participants who have abnormalities of severity grade 3 or greater will be compared between the phytotherapy and placebo arms using Fisher's exact test. A two-sided 0.05 significance level will be used for these comparisons.

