#### 8.2.4 Safety Analysis

Adverse event data will be summarized by treatment arm to capture the proportion of participants reporting at least one episode of a specific adverse event (incidence table), incidence of adverse events causing withdrawal, and incidence of serious adverse events. The total number of episodes for each event reported (frequency table), and the severity and attribution to treatment arm of each episode reported within body system (severity and attribution table), will also be displayed by treatment arm. Listings of adverse events by participants and event will also be provided. Comparisons of incidence of each adverse event between treatment and placebo will be performed using the two-group chi-square test, or Fisher's exact test when the assumptions for the chi-square test are not tenable. A two-sided statistical test with a significance level of 0.05 will be used for these analyses. In addition, 95% confidence intervals will be computed for differences in proportions of adverse events between study arms.

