APPENDIX I - Schedule of Evaluations (Screening Visit 1 - Week 24)

		Screenii	ng Visits				
	PROCEDURE	1	2 (2)	Baseline (2)	Week 4 (7)	Week 12	Week 24
FORM	Informed Consent	X					
CAM01	Eligibility & Randomization			X			
CAM21	Medical History	Х					
CAM22	Medical Follow-Up				Χ	Χ	Х
CAM23/24	Assessment of all medications (1)	Х		X	Χ	Χ	X
CAM31	Vital Signs	Х	Х		Χ	Χ	X
CAM32	Physical & Digital Rectal Exam	X (8)	X (8)				
CAM41	PSA	Х					X
CAM42	Uroflow Measurement	Х	Х			Χ	Х
CAM45	Hematology: CBC/PT/Serum Chemistries	X				Χ	Х
CAM46	Urinalysis	Х					
CAM47	Serum for Banking (3)	Х					
CAM48	EKG (6)	X (6)	X (6)				Х
CAM51	Study Drug Administration & Compliance					Χ	X
CAM61	BPH Outcome Events			AS NEEDED			
CAM62	Permanent Discontinuation of CAMUS Study Assessment (5)				Χ	Χ	X
CAM71	Jenkins Sleep Dysfunction Scale			X			Х
CAM72	Erectile Function			X			X
CAM73	Ejaculatory Function			X			Х
CAM74	Bladder Function		Х			Χ	X
CAM75	International Prostate Symptom Score	X	Х			Χ	X
CAM76	BPH Impact Index		Х			Χ	X
CAM77	Subjective Global Assessment						Х
CAM78	NIH-Chronic Prostatitis Symptom Index			Х			Х
CAM79	Participant Treatment Perception Form (4)						Χ
CAM81	Adverse Events				Χ	Х	Х

1. Assessment of all medications, including over-the-counter medications, every 12 weeks, plus every 4, 28, and 52 week and when an endpoint or adverse event occurs.

2. Screening Visit #2 and Baseline visit can be combined for participant's convenience.

3. Serum samples will be collected at Screening Visit #1 and the last scheduled visit.

4. Subject's guess at whether on active agent or placebo at 24, 48, 72 weeks.

5. Only complete if participant goes completely off study.
6. EKG can be taken at Screening Visit #1 or Screening Visit #2.
7. Visit 4, 28 and 52 can be either in office visit or via telephone interview.

8. Physical & DRE can be done at Screening Visit #1 or Screening Visit #2.

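### Tolerability is part of the primary objective, but no planned analysis identifies men who could not reach or hold a capsule level because of an adverse event, so dose-limiting intolerance could be understated

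*Combined protocol and SAP*

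**What the plan says.** Section 2.1 sets the primary objective as finding out whether the extract "reduces the AUA symptom score compared to placebo over 72 weeks of treatment and is well tolerated". Section 1.1 explains why the second half matters: the trial of double and triple doses is meant to show "whether there is sufficient short-term efficacy and tolerability to merit testing for long-term efficacy".

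Section 5.2 describes what may happen when a man has a side effect. Medication can be interrupted, retitrated from one capsule, or stopped and re-challenged. If the same side effect recurs at a higher dose and a lower one was tolerated, "he can be dropped back to the lower, tolerable dose for the rest of the study".

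Section 8.2.2 states: "The primary endpoint of this study is efficacy as determined by the change in AUA symptom score at 72 weeks". Tolerability has no endpoint, definition or criterion anywhere in section 8.2. The nearest analysis is section 8.2.4: "Adverse event data will be summarized by treatment arm to capture the proportion of participants reporting at least one episode of a specific adverse event", followed by "incidence of adverse events causing withdrawal, and incidence of serious adverse events". That section also plans episode counts, severity and attribution tables, listings, a test of each event between arms, and 95% CIs for differences.

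The laboratory comparison in section 8.2.3 is split into dose levels defined by calendar time ("1-24 weeks = level 1, 25-48 weeks = level 2, 49-72 weeks = level 3"). Appendix I schedules a drug administration and compliance form (CAM51), an adverse event form (CAM81) and a permanent discontinuation form (CAM62). The footnote to CAM62 reads "Only complete if participant goes completely off study".

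**The concern.** A man who fails three capsules, is re-challenged, fails again and finishes on one or two has shown that he does not tolerate the highest dose. He stays in follow-up and on coded medication. His event may be neither serious nor, on a narrow reading, a cause of withdrawal. In the incidence table he looks the same as a man with the same symptom who needed no change. CAM62 does not apply to him because he has not left the study. His capsule counts are collected, but section 8.2 makes no arm comparison of them.

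The decision at stake is the one named in section 1.1: whether two or three capsules a day are tolerable enough to justify a long-term trial. That depends on how many men could stay at those levels, and the planned tables do not give that number.

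**Working it through.** **Plan's own figures.** This point disputes none of them, but 157 per arm is used below, so it was checked first. Section 8.1 gives a 2-point difference, SD 6, one-sided 0.05 and 90% power.
- The normal approximation n = 2(1.645 + 1.282)² × (6/2)² gives 155 per arm.
- The exact t-test power at 157 is 90.4%, so 157 is in order.
- 314/0.90 = 349, against 350 stated.
- The 80% safety power (2.5% v 10%, one-sided 0.05) is reproduced by the continuity-corrected formula, which needs 154 per arm. It concerns severe laboratory events, not ability to hold a dose.

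**What each planned analysis shows about a man who is dropped back.**

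| Planned item | What it shows |
|---|---|
| Adverse event incidence, by arm (8.2.4) | His event, under its own term; not that it limited his dose, nor at which capsule level |
| Episode counts (8.2.4) | The recurrence may add an episode |
| Severity and attribution (8.2.4) | Grade and relationship; not whether the dose was held |
| Events causing withdrawal (8.2.4) | Unclear, because withdrawal is not defined |
| Serious events (8.2.4) | Only if the event was serious |
| Worst laboratory grade per period (8.2.3) | Only grade 3 or greater; if dropped back in weeks 25-48, he still counts as level 3 in weeks 49-72 |
| CAM62 (Appendix I) | Nothing while he remains in the study |
| Capsule counts (5.3, CAM51) | Collected; no analysis in 8.2 |

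**Size, under assumed rates only.** The documents give no expected rate of interruption or drop-back. Take 157 per arm, a two-sided Fisher exact test at 0.05, and 2% of placebo men unable to hold the capsule count due because of an adverse event.

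| Active v placebo | Difference | Power |
|---|---|---|
| 10% v 2% | 8 points | 82.5% |
| 8% v 2% | 6 points | 61.0% |
| 5% v 2% | 3 points | 19% |
| 3% v 2% | 1 point | 3% |

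For 10% v 2%, SE = √[(0.10 × 0.90 + 0.02 × 0.98)/157] = 0.0264. The 95% CI is 0.08 ± 1.96 × 0.0264, or 2.8 to 13.2 points.

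**If withdrawal is read narrowly.** Assume adverse event withdrawals of 2% in both arms, with drop-backs of 0.5% on placebo and 3%, 5%, 8% or 10% on active. The withdrawal comparison alone has about 1% power throughout. Counting withdrawal plus drop-back (2.5% v 5%, 7%, 10% or 12%) gives 13%, 36%, 74% and 89%.

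**If the events are split across terms.** Section 8.2.4 tests each adverse event separately. If the 10% v 2% were spread evenly over three terms, counting only these events, each comparison would be 3.3% v 0.67%, with about 21% power against 82.5% for the combined measure.

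**The case against.** The strongest reply is that these men are not invisible. Their side effects enter the incidence, episode, severity and attribution tables by arm, with tests and confidence intervals, and enter the laboratory table if grade 3 or greater. A reader might infer that no planned analysis counts them at all; section 8.2.4 does not support that. What is missing is their identification as men who could not hold a dose, and any display by capsule level.

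Three further points stand in part.
- Section 5.2 uses withdrawal for withdrawal of medication as well, and its re-challenge steps begin by stopping all study medication. On a broad reading the events-causing-withdrawal table would include these men. The text does not settle this, which is a reason to define the term.
- Drop-back is permitted, not routine. It follows a recurrence on re-challenge. Re-challenge is at the site investigator's discretion, and after a moderate or severe event it needs committee approval. On recurrence the investigator is also told to consider permanent withdrawal, and section 5.8 requires stopping for unacceptable toxicity. The number dropped back may be small.
- The 10% v 2% case is an assumption at the end of the range most favourable to the concern. At 5% v 2% or below, a formal test would have little power, though the proportions and intervals would still inform.

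A reader might also infer that the tolerability question would be answered wrongly in the favourable direction. The plan has no decision rule that would return a finding of tolerated, so that does not follow. The gap is in what is summarised; it is not a biased test.

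**Conclusion.** The point holds as a gap in the tolerability analysis. Half of the primary objective has no defined measure, section 5.2 creates a form of intolerance short of leaving treatment, and section 8.2 has no comparison of interruption, reduction, failure to escalate or capsule count held. Intolerance of two or three capsules could be understated, because it would show only as separate adverse event terms by arm.

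The size is unknown. Under the assumed rates, a combined measure would have from 3% power (3% v 2%) to about 83% (10% v 2%) at 157 per arm. The efficacy analysis and sample size are unaffected, and no judgement is made on the dosing rules in section 5.2.

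**What to change.** In section 8.2.4:
1. Name as the tolerability measure the proportion of randomised men in each arm who, because of an adverse event, interrupted, reduced, did not escalate or permanently stopped coded medication. Give it for each capsule level and overall, with the between-arm difference and 95% CI.
2. Define withdrawal in the existing table, stating whether temporary stopping and drop-back count.
3. Report by arm the proportion taking the capsule count due under the protocol at weeks 24, 48 and 72. List separately the men whose schedule lags only because section 5.2 lets a successfully re-challenged man complete 24 total weeks at his dose before escalating. Without that separation, a fixed-week check would class men who tolerate the drug as failures.

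The sources are CAM51 and CAM81, which are already scheduled. The form contents are not in the documents, so a reason-for-change field may be needed. The cost is one or two extra tables and possibly that field, with no added visits or participants.

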#### **5.3** Measures of Compliance

Participants will be instructed to bring their packaged coded medication to each follow-up visit. Capsule counts will be conducted to assess the participant's level of compliance with the treatment regimen. The use of blister packs will greatly facilitate keeping CAMUS study personnel blinded to the treatment assignments of their participants.

Participants will be supplied ample study capsules at each visit and assured that they should have capsules left over at the following visit. Participants will be asked to return their remaining blister-pack cards with remaining capsules at each visit for pill count and compliance check. Participants demonstrating consistently inadequate adherence (>20% of capsules remaining on at least two consecutive visits) will be counseled regarding measures to improve adherence (including regular telephone or mail reminders) and will

have a visit with the site principal investigator or co-investigator, if necessary. If participants miss a dose of their study medication, they will be instructed *not* to take an extra dose the next day.

There are no known serum markers for *Serenoa Repens* that would permit assessment of whether participants in the active or control groups are taking the study medicine obtained from non-study sources. Visit adherence will be monitored carefully. Participants demonstrating frequent missed visits or out-of-window visits will be contacted by the Site Coordinator or PI to discuss barriers to keeping scheduled study visit appointments.

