#### 4.3 Evaluations during Treatment and Follow-Up

- 4.3.1 Focused physical examination (including height and weight) and digital rectal examination at the 72 week visit.
- 4.3.2 Medical follow-up to include new diagnoses, treatments, hospitalizations, life events at the 4, 12, 24, 28, 36, 48, 52, 60 and 72 week visits.
- 4.3.3 Hematology: CBC and PT at the 12, 24, 36, 48, 60 and 72 week visits.
- 4.3.4 Serum chemistries: serum creatinine sodium, potassium, chloride, bicarbonate, glucose, ALT (SGPT), AST (SGOT) and GGT at the 12, 24, 36, 48, 60 and 72 week visits.
- 4.3.5 Urinalysis, including dipstick at the 72-week visit. If dipstick is positive (greater than 0) for blood or leukocyte esterase, then a specimen will be sent for microscopic analysis.
- 4.3.6 PSA at the 24, 48, and 72 week visits. The PSA measurements will be determined by a central laboratory. Please refer to the Manual of Operations for specimen collection and shipping instructions.
- 4.3.7 Vital signs at the 4, 12, 24, 28, 36, 48, 52, 60 and 72 week visits. (Visits 4, 28 and 52 can be optional phone interviews. A blood pressure monitor will be provided to participants to record blood pressure at home. The participant must agree to give 2 sitting readings to the study personnel.)
- 4.3.8 Uroflow measurement to include: voiding time, flow time, time to maximum flow, peak flow rate, mean flow rate, voided volume and post void residual at the 12, 24, 36, 48, 60 and 72 week visits.

- 4.3.9 Bladder Function, IPSS (AUA Symptom Score plus IPSS Quality of Life questions), and BPH Impact Index questionnaires, at the 12, 24, 36, 48, 60 and 72 week visits.
- 4.3.10 Erectile Function, Ejaculatory Function, NIH-CPSI, Jenkins Sleep Dysfunction Scale and Subjective Global Assessment, and participants' perception about whether they are on active therapy or placebo at the 24, 48, and 72 week visits.
- 4.3.11 Treatment compliance by pill count and provision of assigned study medication at the 12, 24, 36, 48, 60, and 72 week visits.
- 4.3.12 Adverse event assessment at the 4, 12, 24, 28, 36, 48, 52, 60, and 72 week visits.
- 4.3.13 Assessment of all medications, including over-the-counter medications, at the 4, 12, 24, 28, 36, 48, 52, 60 and 72 week visits, or when and adverse event occurs. (Visits 4, 28, and 52 can be omitted if optional phone interview chosen.)
- 4.3.14 Serum for banking at SV1.0 and 72 week visit.

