## 5.4 Packaging of Medications and Supplies *Serenoa Repens* 320 mg capsules and matching placebo will be supplied in blister cards.

A kit will be prepared that will contain enough blister cards to allow for a 12-week supply plus 2 weeks. All blister cards and kits will be labeled in a manner to maintain the blind. The kits will be prepared as per section 5.1 for each of the two treatment assignments.

Each site will be sent an initial supply of kits. Kits will be assigned to participants at randomization. Additional kits will be sent to replace those assigned to participants and for the next visit for randomized participants. Additional kits will be available to be assigned to participants in the event of lost or damaged medication.

Participants will be instructed to take one capsule from the study drug package daily for the first 24 weeks, two capsules from the study drug package daily for the 2nd 24 weeks, and three capsules from the study drug package daily for the last 24 weeks. Participants will be instructed to return all used, partially used and unused blister cards to the study coordinator at the next visit, to allow for compliance counts. Medication returned by participants will be documented in their case report forms. Returned medication once documented may be destroyed on site according to site-specific procedures on file with the Data Coordinating Center.

Kits that expire or kits from participants who are dropped permanently from the study will be disposed of at each clinical site according to site-specific procedures on file with the Data Coordinating Center.

Unmasking of kits should not be necessary but in the event of a medical emergency the site should contact the Data Coordinating Center.

All medication kits will be shipped with an invoice, which should be checked to ensure the shipment is complete and undamaged. Any missing, or incorrect or damaged kits should be documented on the invoice and the Drug Distribution Center contacted immediately. The invoice should be signed by an authorized site representative and returned to the Drug Distribution Center (by Fax or Mail); a copy should be maintained in the site drug inventory record book. All kits assigned to participants should be signed out of the drug accountability records.

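### The two-consecutive-count adherence trigger in section 5.3 is first met at the end of the dose level for under-dosing that starts at an escalation (week 72 at triple dose), and its 20% cut-off has no defined denominator

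*Combined protocol and SAP*

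**What the plan says.** The only written adherence trigger is in section 5.3: "Participants demonstrating consistently inadequate adherence (>20% of capsules remaining on at least two consecutive visits) will be counseled regarding measures to improve adherence". A visit with the site investigator may follow if necessary.

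Section 4.3.11 fixes when counts are made: "Treatment compliance by pill count and provision of assigned study medication at the 12, 24, 36, 48, 60, and 72 week visits". Form CAM51 in Appendix I shows the same six weeks. The contacts at weeks 4, 28 and 52 may be by phone (section 4.3) and carry no CAM51 entry.

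The dosing steps are in section 5.1: "All participants will take one gelcap daily for the first 24 weeks, two gelcaps daily in the second 24 weeks and three gelcaps daily". The third step covers weeks 49 to 72. Coded medication stops at the week 72 visit (section 4.4), which is also when the primary endpoint is read (section 8.1).

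On supply, section 5.4 says: "A kit will be prepared that will contain enough blister cards to allow for a 12-week supply plus 2 weeks". Section 5.3 makes the surplus deliberate: "Participants will be supplied ample study capsules at each visit and assured that they should have capsules left over at the following visit". No section says what the percentage of capsules remaining is a percentage of, or names a target share of doses to be taken.

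**The concern.** The trial was set up to test double and triple doses after an earlier trial at 320 mg found no effect (section 1.1). Its primary endpoint is read at the end of the triple-dose period. The number of gelcaps to be taken rises at weeks 24 and 48, so these are natural points for under-dosing to begin. A trigger that needs two bad counts, where each level has only two, cannot require action on such a man until the level is finished.

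Capsule counts are the only measure of intake that section 5.3 describes. The primary population keeps every randomized man who meets the major eligibility criteria and took at least one dose (section 8.2.1). Men who never step up therefore stay in the week 72 comparison and would pull the contrast towards that of a lower dose.

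The undefined denominator is a smaller matter, but different sites could apply the same cut-off quite differently.

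**Working it through.** **The plan's own figure.** Section 8.1 assumes a 2-point difference, SD 6, a two-group t-test, one-sided 0.05 and 90% power. Recomputing gives 155 per arm against the stated 157, and power of 90.5% at 157. For dropout, 314/0.90 = 349, against 350 stated. The sample size reproduces and is not in dispute.

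**Timing.** Inputs: counts at weeks 12, 24, 36, 48, 60 and 72 (4.3.11, Appendix I); levels starting at weeks 0, 24 and 48, each lasting 24 weeks (5.1); two consecutive counts needed (5.3).

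| Under-dosing starts | First two counts | Trigger first met | Level ends | Weeks of level left | Weeks left if one count sufficed |
|---|---|---|---|---|---|
| Week 0 | 12, 24 | 24 | 24 | 0 | 12 |
| Week 24 | 36, 48 | 48 | 48 | 0 | 12 |
| Week 48 | 60, 72 | 72 | 72 | 0 | 12 |

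The first bad count would be hard to miss. A 14-week kit holds 14 × 7 = 98 capsules for each gelcap per day, that is 98, 196 or 294 by level.
- Still on one of two gelcaps: (196 − 84)/196 = 57.1% left at week 36; rule met at week 48.
- Still on two of three gelcaps: (294 − 168)/294 = 42.9% left at week 60; rule met at week 72.

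**Denominator.** Let *a* be the share of due doses taken. In weeks of supply, 14 are dispensed, 12 are due and 14 − 12*a* remain. More than 20% remaining then means:
- Share of capsules dispensed (the plain reading): (14 − 12*a*)/14 > 0.20, so *a* < 0.80 × 14/12 = 93.3%.
- Share of the 12-week requirement, surplus left in: (14 − 12*a*)/12 > 0.20, so *a* < (14 − 2.4)/12 = 96.7%.
- Surplus removed first: (12 − 12*a*)/12 > 0.20, so *a* < 80%.

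On the plain reading, full adherence over exactly 12 weeks leaves 2/14 = 14.3%, which is below the cut-off.

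**Illustration only.** Suppose a share *p* of the active arm does not step up. If these men contribute no effect, the expected difference is 2(1 − *p*). If they keep half the effect, it is 2(1 − *p*/2). With 157 per arm, SD 6 and one-sided 0.05:

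| *p* (assumed) | No effect: difference, power | Half effect: difference, power |
|---|---|---|
| 5% | 1.9, 88% | 1.95, 89% |
| 10% | 1.8, 84% | 1.9, 88% |
| 20% | 1.6, 76% | 1.8, 84% |

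These are losses from not stepping up at all. The trigger rule accounts only for the part that a contact at week 60 would have recovered, and the documents give nothing from which to estimate that part.

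**The case against.** **Staff may act sooner.** Section 5.3 says when counseling is required and does not forbid it earlier. Staff see the week 36 and week 60 counts, and a committee monitors adherence (section 10.4.4). This stands, and it rules out the inference that a failure to step up cannot be corrected within its level. But neither route has a stated threshold or timing, so the written rule is the only one that sites are bound to follow.

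**Some men are caught earlier.** If the count at week 24 or 48 was already low, the trigger is met at week 36 or 60. Counseling at week 48 also still precedes the triple-dose period. Both are right. The gap concerns under-dosing that begins at an escalation, and it matters most at week 48.

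**Section 5.3 can be read as counting more often.** It has cards returned "with remaining capsules at each visit for pill count and compliance check", which might take in weeks 28 and 52. But section 4.3.11 and Appendix I schedule no count then. Four weeks into a kit a fully adherent man still holds 10/14 = 71.4%, so the cut-off could not work there.

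**The cut-off and the kit do not contradict each other.** A reader might infer that they do, or that adherent men will be flagged. Full adherence leaves 14.3%. A man seen at 11 weeks returns 21/98 = 21.4%, but one such visit flags nobody. If his next visit is at week 24, that interval is 13 weeks and he returns 7/98 = 7.1%. At full adherence he would need two successive intervals of at most 78 days, 156 days in all against 168. A contradiction would also need an 80%-of-doses target, which the documents never state. A man who, under section 5.2, "he can be dropped back to the lower, tolerable dose for the rest of the study" would exceed the cut-off only if still supplied from larger kits, and the documents do not say how he is supplied. A false flag costs a conversation; no analysis population depends on adherence.

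**The power figures have no source.** The 5% to 20% rates are assumed, the earlier trial reported excellent adherence (section 1.2), and a man on two of three gelcaps still takes 640 mg. A reader should not infer that this rule costs the trial up to 14 points of power.

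**Conclusion.** The timing point holds. For a previously adherent man whose under-dosing begins at an escalation, the written trigger is first met at week 48 or week 72, with none of that dose level left. At triple dose, this is the visit at which drug stops and the primary endpoint is measured. The result rests only on the visit schedule, the 24-week levels and the two-count wording. How much this costs the trial is unknown, because it depends on how many men fail to step up and how often staff act before the rule requires it.

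The secondary point holds as an ambiguity: the cut-off does not say how the planned two-week surplus is treated, and it can mean anything from under 80% to under 96.7% of due doses. On the plain reading (93.3%) it is stricter than it looks, which leans towards flagging more men, the opposite direction to the delay.

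Neither point touches the primary test or the sample size. This is a cheap improvement to conduct.

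**What to change.** In section 5.3:
- Trigger the adherence contact on the first count beyond the cut-off, at least for the first count after each escalation (weeks 36 and 60). That leaves 12 weeks of the level.
- Ask how many gelcaps are taken per day at the existing week 28 and week 52 contacts, by phone or in the office.
- Define adherence as capsules taken divided by capsules due, from the actual days since dispensing and the gelcaps per day assigned to that man at the time. The planned surplus and any early or late visit then drop out of the calculation. The sponsor should confirm the intended cut-off on that scale.

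The cost is protocol wording, a change to the CAM51 calculation, one added question at two contacts, and some extra reminder calls to men with a single low count. No new visit is needed, and the dosing and analysis are unchanged.
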